### **Exploratory Outcome Variables**

Questionnaire-based outcomes comparing Baseline to 52 weeks will be analyzed using a linear regression model with a separate intercept for each subject, a dichotomous time-point effect, and a multiplicative interaction between time-point and treatment.

Changes in texture-based quantitative analysis of CT progression of fibrosis will be analyzed using multinomial regression with a separate intercept for each subject, a dichotomous time-point effect, and a multiplicative interaction between time-point and treatment.

Statistical analyses of RNA-seq and ChIP-seq results from PBMC samples will be performed with the DESeq2 package in the R language. The p-values of Wald tests for differential expression will be adjusted using the Benjamini-Hochberg false discovery rate procedure to account for multiple testing after filtering out genes with mean normalized counts below a threshold. Significantly differentially expressed genes will be assigned to biochemical pathways and functional categories using KEGG and Gene Ontology databases using tools including GATHER, DAVID, R packages such as KEGGprofile and topGO, as well as Ingenuity pathway analysis. Diversity of immune cell types will be derived from the gene expression profiles of each sample to ensure valid comparisons and modeling. Expression profiles (baseline and week 52) will be correlated within the two HP arms using an ANOVA analysis.

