### *Key Secondary Efficacy Outcome Variables*

1. Progression-free survival (PFS) defined as the time from study treatment randomization to the first occurrence of any of the following events:
  - a. Relative decline from baseline in  $\geq 10\%$  in FVC and/or DLCO
  - b. Acute exacerbation of FHP defined as acute respiratory declined leading to hospitalization or ER or Urgent care evaluation; or evidence of all of the following criteria within a 4-week period in the outpatient setting:
    - i. Increase from baseline  $\text{FIO}_2 \geq 1 \text{ L O}_2$ .
    - ii. Clinically significant worsening of dyspnea and/or cough.
    - iii. New, superimposed ground-glass opacities or consolidation or new alveolar opacities on chest x-ray or CT.
    - iv. Primary: if all other causes excluded (e.g., acute gastro-esophageal aspiration, pneumothorax, infection, left heart failure, pulmonary

embolism, or identifiable cause of acute lung injury).

- c. A decrease from baseline of at least 50 meters in 6-minute walk distance.
- d. Change in background therapy (need for a new course of PO or IV steroids or for the patient receiving maintenance prednisone, as a need to increase the dose by 10 mg or more; and/or addition of cyclophosphamide, azathioprine, mycophenolate mofetil or mycophenolic acid).
- e. Death

2. Slope of FVC over 52-week treatment period.
3. Mean change in %DLCO at week 52
4. Proportion of patients with all-cause mortality.
5. Proportion of patients with all-cause hospitalization.
6. Proportion of patients with hospitalization for respiratory cause.
7. Proportion of patients with respiratory exacerbations requiring hospitalizations.
8. Proportion of patients with evidence of progression in fibrosis on visual comparison of baseline and week 52 HRCT scans.

*Exploratory Outcome Variables:*

1. Mean change from baseline in health-related quality of life, measured by St. George's Respiratory Questionnaire (SGRQ) (3 domain scores and total score), at Week 52.
2. Mean change from baseline in health-related quality of life, measured by A Tool to Assess Quality of Life Questionnaire (L-IPF) at Week 52.
3. Mean change from Baseline to Week 52 in dyspnea as measured by the University of California at San Diego Shortness-of-Breath Questionnaire (UCSD SOBQ) score.
4. Proportion of patients with evidence of progression, stability or improvement in fibrosis on texture-based quantitative analysis of CT.

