#### **Week 13 ( $\pm$ 2 weeks)**

The following will be performed at Week 13:

1. Directed history (including review of AEs/SAEs, concomitant medications, oxygen use, hospitalizations, dosing, and diary).
2. Physical examination, vital signs, FiO2 and weight.

3. ECG.
4. Spirometry (FVC, FEV1).
5. Clinical laboratory assessments, including hematology, serum chemistries, pregnancy test for women of childbearing capacity.
6. 6MWT with Borg Scale pre and post.
7. UCSD SOBQ, L-IPF and SGRQ.
8. Collection of any unused study treatment, review compliance and dispensing of 13-week supply of study treatment.
9. Dispense new diary, if required.
10. Vital Status Assessment.

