### **Sample Size and Power Considerations**

The sample size and power calculations for this study are based on the primary endpoint, mean change in %FVC from Baseline to Week 52. Estimates are based on the results from the National Jewish Health pilot data of FHP (N=30 patients with biopsy and HRCT FHP pattern). For the primary efficacy comparison of change in mean %FVC between the treatment (2403 mg/d) and placebo groups, about 13 patients in the placebo and 25 (N=38) in the treatment group will provide at least 85% power to detect a mean difference between groups of 2%. Assuming a 10% attrition rate approximately 42 subjects will be enrolled and randomized in a 2:1 ratio to pirfenidone 2403 mg/d or placebo.

These calculations assume a standard deviation in the %FVC change from baseline to 52 weeks of 2% and are based on a 2-sample means t-test with a 2-sided Type I error probability of 0.05.

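### As most naturally read, the questionnaire model is an unadjusted change-score comparison; adding the baseline score would make it more precise at almost no cost

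*Combined protocol and SAP*

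**What the plan says.** The analysis is described under Statistical Methods, Exploratory Outcome Variables: "Questionnaire-based outcomes comparing Baseline to 52 weeks will be analyzed" using a "linear regression model with a separate intercept for each subject", together with "a dichotomous time-point effect, and a multiplicative interaction between time-point and treatment". No baseline covariate is listed, and the intercepts are not labelled fixed or random.

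The matching endpoints, listed as exploratory under Study Endpoints, are changes to Week 52; the UCSD SOBQ entry, for example, reads "Mean change from Baseline to Week 52 in dyspnea". The visit schedules for Day 1 and Weeks 13, 26, 39 and 52 each list "UCSD SOBQ, L-IPF and SGRQ", so the three intermediate assessments are collected but have no specified analysis.

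Other outcomes are handled differently. The primary %FVC model and the %DLCO model include ranked baseline as a covariate, and the FVC slope model includes baseline FVC. A supportive %FVC analysis uses all visits in a mixed-effects repeated-measures model. Multiple imputation is described only under the primary analysis.

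**The concern.** A model with one intercept per patient and two time points uses only the within-patient difference. The baseline score is subtracted in full and never used as a predictor, so a chance baseline difference between arms of about 28 and 14 patients passes into the estimated effect through regression to the mean. Baseline adjustment removes that part of the noise. The plan already does this for FVC and DLCO and gives no reason for treating the questionnaires otherwise.

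At stake is the width of the confidence intervals for three patient-reported outcomes in a small trial. The validity of the comparison is not at stake.

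**Working it through.** **Inputs.** From Sample Size and Power Considerations: "approximately 42 subjects will be enrolled and randomized in a 2:1 ratio to pirfenidone 2403 mg/d or placebo", which is 28 and 14; "Assuming a 10% attrition rate", with 38 evaluable (25 and 13). The documents give no standard deviation, correlation or power for the questionnaires, so there is no stated figure to reproduce. The baseline to Week 52 correlation r is an assumption, shown over a range. Equal variance s² at the two times is also assumed.

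**Step 1: what the model estimates with fixed intercepts.** Write Y(i,t) = a(i) + b·t + d·t·T(i) + error, with t = 0 or 1 and T = 1 for pirfenidone. Differencing within patient removes a(i) and leaves change(i) = b + d·T(i) + error. The estimate of d is therefore the difference in mean change between arms. Degrees of freedom agree: 84 observations − 42 intercepts − 2 terms = 40 = 42 − 2. In a simulated 42-patient data set, the subject-intercept model and the t-test on change gave the same estimate (−0.1343), p-value (0.5325) and degrees of freedom (40). A patient with no Week 52 score has one observation, which the patient's own intercept absorbs, and so adds nothing to d.

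**Step 2: variance relative to baseline adjustment.** The per-patient variance of change is 2(1−r)s². The residual variance after adjusting for baseline is (1−r²)s². The ratio is 2(1−r)/(1−r²) = 2/(1+r). Estimating one covariate in two groups inflates the adjusted variance on average by 1 + 1/(N−4) = 1 + 1/34 = 35/34 at N = 38, so the net ratio is 2/(1+r) × 34/35.

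| r (assumed) | 2/(1+r) | net of covariate cost |
|---|---|---|
| 0.5 | 1.333 | 1.295 |
| 0.7 | 1.176 | 1.143 |
| 0.8 | 1.111 | 1.079 |
| 0.9 | 1.053 | 1.023 |

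The square roots of the net ratios give intervals about 14%, 7%, 4% and 1% wider.

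Simulation with 28 and 14 patients, 400 runs at each r, gave adjusted-to-change-score variance ratios of 0.74, 0.89 and 0.95 at r = 0.5, 0.7 and 0.8, against large-sample values of 0.75, 0.85 and 0.90.

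**Step 3: the random-intercept reading.** With random intercepts and no treatment main effect, the model forces the two arms to share one baseline mean, which itself acts as a baseline adjustment. Its simulated variance ratios to the change score were 0.74, 0.89 and 0.93, about the same as ANCOVA.

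**Step 4: what Weeks 13, 26 and 39 add to the Week 52 contrast.** This was calculated for r = 0.5 to 0.8, with compound-symmetric and autoregressive-type correlation and monotone dropout.

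- Complete data: no gain (ratio 1.0).
- 10% attrition, no baseline adjustment: ratio 0.954 to 0.972, a gain of about 3–5%.
- 10% attrition, on top of baseline adjustment: ratio 0.964 to 0.988, a gain of about 1–4%.
- Both changes together at 10% attrition: ratio 0.73 to 0.88 against the change score.

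**The case against.** The strongest objection is that the intercept type is not stated. The next sentence of the same section uses the same intercept wording for a multinomial model of the CT data. Ordinary fixed patient intercepts behave badly there with two time points, which hints at random effects. If random intercepts were meant, the analysis is not unadjusted and Step 3 shows little is lost.

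This stands as a limit on the point, but it does not make random intercepts the natural reading. The plan names mixed effects or random coefficients where it uses them for FVC. The missing treatment main effect also fits fixed intercepts, which would absorb that term.

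It is also fair to say that the endpoints are defined at Week 52, so a Week 52 contrast matches them. Patients who stop treatment are asked to continue assessments, which limits missing data. No decision rule or power claim rests on these outcomes, and adjusting FVC for baseline does not oblige the plan to adjust questionnaires.

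A reader might infer that leaving out three collected visits costs a lot of precision. Step 4 does not support that: the 2/(1+r) figure comes wholly from the missing baseline adjustment, and the interim visits matter only when Week 52 is missing. A reader might also infer bias. Under randomization the change score is unbiased with complete data, and its standard error already reflects chance baseline imbalance.

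**Conclusion.** The point holds as a minor efficiency improvement. On the fixed-intercept reading, the questionnaire analysis is an unadjusted change-score comparison. Its variance exceeds that of a baseline-adjusted analysis by about 33%, 18% or 11% in theory for r = 0.5, 0.7 or 0.8. After the covariate cost at N = 38 the excess is roughly 29%, 14% or 8%, and by r = 0.9 it is only about 2%.

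These sizes rest on an assumed correlation and equal variances, neither of which the documents give. They largely vanish if random intercepts were intended. The interim visits are a small extra, worth about 1–5% of variance at the planned attrition.

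The documents do not support calling the analysis invalid, or saying that it is certainly unadjusted. What is certain is that the intercept type is unstated and that no baseline covariate is named.

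**What to change.** Replace the questionnaire model under Exploratory Outcome Variables with a regression of Week 52 change on treatment and baseline score, fitted for each score, and report the Week 52 treatment difference with its 95% confidence interval.

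An equivalent option is a repeated-measures model of change at Weeks 13, 26, 39 and 52 with treatment, visit, treatment-by-visit and baseline score, from which the same Week 52 contrast is taken. It also uses patients whose Week 52 score is missing. If it is chosen, name the covariance structure in advance, since only about 13 evaluable placebo patients are expected.

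If the sponsor prefers to keep the present model because random intercepts were meant, the SAP should say so explicitly.

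The cost is a few lines of SAP wording and minor programming. No new data, visits or patients are needed, and the endpoint definitions do not change.

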### **HRCT Scans**

HRCT scans obtained within 4 months before the Screening period as part of the standard of care for a patient may be used to confirm eligibility, provided they meet all of the image acquisition and quality criteria required by the CT expert readers. All HRCT digital images are to be stored on a dedicated disk. The images will be anonymized using a tool developed by the Quantitative Imaging Laboratory at National Jewish Health. The Quantitative Imaging Laboratory will be tasked with interpretation, archiving, and quantitative analysis of the images. One thoracic radiologist with expertise in FHP will review the HRCT scans using an electronic score sheet. Data regarding the HRCT interpretation will be entered electronically

into the trial research's database and incorporated into the clinical database. Evidence of progression, stability, or improvement in fibrosis on temporally blinded visual comparison of baseline and week 52 HRCT scans will be documented on a five-point scale (much better, better, same, worse, and much worse).

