### **Screening Period**

The Screening period is defined as the time between the date of the first Screening procedure and may last up to 30 days. Screening procedures may be conducted on different days within the Screening period if convenient.

The following procedures will be performed during Screening:

1. Written informed consent, if not already obtained during the Washout Period.
2. Complete medical history, review of systems, and review of concomitant medications.
3. Physical examination, vital signs, weight, and height.
4. Clinical laboratory assessments, including hematology, serum chemistries, serologic tests clinically within the past 30 days, and pregnancy test for women of childbearing capacity.
5. ECG.
6. Resting Oxygen and FIO2.
7. A 6MWT with Borg Scale pre and post.
8. Transfer of all surgical lung biopsies, if available, for evaluation by pathologist.
9. Review of transbronchial biopsy and/or BAL, if available, to assess eligibility
10. HRCT within the past 4 months, spirometry and DLCO within the past 30 days to assess eligibility.

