### **Key Secondary Efficacy Outcome Variables and Analyses**

Multiplicity adjustment will be performed across all secondary endpoints.

Progression-free survival will be compared between the pirfenidone 2403 mg/d and placebo groups using the log-rank test. A proportional hazards model will be used to estimate the hazard ratio. Descriptive analysis of progression free survival will be presented using Kaplan-Meier curves. Mortality will be analyzed using logistic regression with a treatment effect and accounting for potential over- or under-dispersion in the outcome.

The slope for annual rate of FVC decline will be analyzed using a random coefficient regression model with treatment and baseline FVC as covariates.

DLCO will be analyzed using a rank linear regression model with the rank change in %DLCO

from Baseline to Week 52 as the outcome variable and rank Baseline %DLCO and HP therapy as covariates.

Non-elective hospitalization from any cause and CT progression of fibrosis will be compared between the pirfenidone 2403 mg/d and placebo groups using logistic regression accounting for possible over- or under-dispersion in the outcome.

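### The model planned for the CT-texture endpoint needs an outcome at two time points, but the endpoint gives one change category per patient

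*Combined protocol and SAP*

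**What the plan says.** - **Endpoint.** Under Study Endpoints, exploratory outcome 4 is "Proportion of patients with evidence of progression, stability or improvement in fibrosis on texture-based quantitative analysis of CT".
- **Model.** Under Statistical Analyses, Exploratory Outcome Variables, the text reads "Changes in texture-based quantitative analysis of CT progression of fibrosis will be analyzed using" and then "multinomial regression with a separate intercept for each subject, a dichotomous time-point effect, and a multiplicative interaction between time-point and treatment". It does not say whether the subject intercepts are fixed or random, or what one row of the data set is.
- **Same structure elsewhere.** The paragraph just before it uses the same three terms, in a linear model, for the questionnaires. Those are collected on Day 1 and at Week 52.
- **Scans.** The Screening Period asks for "HRCT within the past 4 months, spirometry and DLCO within the past 30 days to assess eligibility", and the Week 52 list includes an HRCT. The lists for Day 1 and Weeks 3, 5, 13, 26 and 39 include none.
- **Reading of scans.** In HRCT Scans, a "temporally blinded visual comparison of baseline and week 52 HRCT scans will be documented on a five-point scale". That scale belongs to the visual read. For the quantitative work the section says "The Quantitative Imaging Laboratory will be tasked with interpretation, archiving, and quantitative analysis of the images"; it gives no rule for the three categories.
- **Visual CT endpoint.** Under Key Secondary Efficacy Outcome Variables and Analyses, "CT progression of fibrosis will be compared between the pirfenidone 2403 mg/d and placebo groups using logistic regression". No time term or subject intercept is mentioned there.

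**The concern.** Progression, stability and improvement each describe a comparison of two scans. Two scans therefore give one category per patient, and that category does not exist at baseline. A dichotomous time-point effect has nothing to contrast unless each patient has an outcome at both times. The structure suits the questionnaires, which have a score at each visit, and it appears to have been carried over to an outcome that does not.

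An analyst who follows the text must supply at least two things that it leaves open: what the response is on each row, and how texture output becomes a category. With about 14 placebo patients, either choice could move the result. If they are made after unblinding, the reported odds ratios cannot be called pre-specified.

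**Working it through.** The plan states no power, sample size or alpha for this endpoint, so there is no figure to reproduce. The check is whether a treatment effect can be estimated under each reading of the model.

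**Inputs.** Study design: about 42 patients randomised 2:1, so 28 and 14. Sample Size and Power Considerations: 25 and 13 after attrition. The design matrix below applies to each of the two logits of a three-category outcome.

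**1. One row per patient, fixed subject intercepts.** The columns are n subject indicators, time, and time × treatment. Every row is at Week 52, so time = 1 throughout.
- Time equals the sum of all subject indicators.
- Time × treatment equals the sum of the pirfenidone subjects' indicators.
- n = 42: 42 rows, 42 + 2 = 44 columns, rank 42. The indicators alone already have rank 42.
- n = 38: 38 rows, 40 columns, rank 38.

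Both terms are fully aliased. In a binary version (progression or not), the profile log-likelihood is 0 at treatment coefficients of −3, 0 and +3, so the data carry no information on treatment.

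**2. Two rows per patient, every baseline coded as stable.** The subject intercepts are removed by conditioning. Patients who stay stable contribute nothing. Each patient who changes contributes −log(1 + exp(−(b + g × treatment))), where b is the time effect and g the treatment term, both taken as common to the two logits. Invented counts for improvement/stability/progression: 6/14/8 on pirfenidone and 3/5/6 on placebo, so 14 and 9 patients change.

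| b | log-likelihood at g = −2 | at g = 2 | range |
|---|---|---|---|
| 2 | −10.846 | −1.396 | 9.45 |
| 5 | −0.741 | −0.073 | 0.67 |
| 10 | −0.0051 | −0.0005 | 0.005 |
| 20 | 0.000 | 0.000 | 0.000 |

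For b = 2 and g = −2: 9 × (−0.1269) + 14 × (−0.6931) = −10.846. The likelihood climbs towards 0 as b grows, whatever g is. There is no finite maximum, and g is not determined.

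**3. One row per patient, random intercepts.** The fixed part has three columns (intercept, time, time × treatment) and rank 2. Time duplicates the intercept, while time × treatment becomes the treatment indicator and raises the rank from 1 to 2. Once time is dropped the arms can be compared. There remain 2 intercepts + 2 treatment effects + 1 standard deviation = 5 parameters against 2 arms × 2 free probabilities = 4. Equal arm probabilities give zero treatment logits at standard deviations of 0, 1 and 2, so the null hypothesis can be tested. The size of the odds ratios depends on a variance that the data cannot identify.

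**4. Two rows per patient, a category observed at each scan.** 84 rows, 44 columns, rank 44. The model as written is identifiable by design. It needs a category for each scan, which the documents do not define.

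**5. One row per patient, common intercept and treatment.** Two columns, rank 2, and 4 parameters against 4 free probabilities. With assumed counts for progression/stability/improvement of 8/17/3 and 7/6/1, the treatment log odds ratio for progression against stability is log(8/17) − log(7/6) = −0.91. Its standard error is √(1/8 + 1/17 + 1/7 + 1/6) = 0.70. Both are finite.

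**The case against.** The strongest reply is that time, subject intercepts and an interaction presuppose two observations per patient, and that exactly two scans are scheduled. The first three exploratory outcomes, on the questionnaires, are also worded as change from baseline, and the plan analyses them with this same structure. There the interaction estimates the difference in change. So the word *changes* in the CT sentence does not by itself show that one change value per patient is the response. This stands as far as it goes. It does not rescue the CT endpoint, because its three labels are themselves comparisons of two scans, and nothing defines a category for a single scan.

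A reader might infer that the plan, as written, can return no treatment effect. The documents do not support that without conditions. It requires one row per patient and fixed intercepts, and the plan states neither. Subject-specific intercepts are often fitted as random, and step 3 shows that the arms can then be compared. Even so, the time term has to go, so the written model still has to change.

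A reader might also infer that no category rule exists. The quantitative analysis is assigned to an imaging laboratory whose own documents are not reproduced, so the rule may be held there. The point is only that the protocol and SAP do not state it.

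Finally, the endpoint is exploratory, with no alpha or power attached. That is correct and limits the weight of the point.

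**Conclusion.** The mismatch is real. The endpoint is one change category per patient, while the planned model needs an outcome at each of two time points. Failure to estimate any treatment effect is one consequence, under the reading with a single row and fixed intercepts (rank 42 of 44 columns, or 38 of 40). Coding every baseline as stable does not repair it. The two readings that do work either alter the written model (random intercepts, time dropped) or alter the endpoint (a category per scan).

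Confidence is moderate, because the plan leaves the row layout and the type of intercept open. The scope is one exploratory endpoint. The primary analysis is untouched, and so is the visual CT analysis, which already uses a between-arm model. This is a low-priority correction, worth making because it is cheap.

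**What to change.** In Statistical Analyses, Exploratory Outcome Variables:

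1. State that the response is the single Week 52 change category, one row per patient. Keep the multinomial regression with treatment as the between-arm term, for example with stability as reference, and delete the subject-intercept and time terms.
2. State before unblinding how texture output becomes progression, stability or improvement, or cite the imaging laboratory's document that does so. The Unblinding section releases assignments only after the final analysis, so there is time.
3. Report the three proportions per arm, the odds ratios with 95% confidence intervals, and the number of missing Week 52 scans per arm.
4. Say what is reported if a category is empty in one arm, since the matching odds ratio is then not finite. If 10% of placebo patients improve (an assumption), the chance that none of 14 does is 0.9^14 = 0.23.

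Proportional odds is an option. It uses one odds ratio for all three categories but adds the assumption that a single ratio holds. Present the result as an estimate. For assumed placebo splits (improvement/stability/progression) of 10/30/60, 20/40/40 and equal thirds, with no true effect, the large-sample standard error of the log odds ratio is 0.62 to 0.67 (28 against 14). The 95% interval then runs from about 0.27–0.30 to 3.3–3.7.

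Alternatively, if the software gives a continuous fibrosis score per scan and that is what is meant, name that score as the outcome and use a baseline-adjusted or repeated-measures linear model. Amend exploratory outcome 4 to match.

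Cost: SAP wording and a little programming. No new data or visits are needed.

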### **RANDOMIZATION AND BLINDING**

This is a randomized, double-blind, placebo-controlled study. Neither study personnel nor the subjects will know which study treatment the subject is receiving. Subjects will be randomized in a 2:1 ratio to receive either pirfenidone 2403 mg/d or a placebo equivalent. The placebo will be visually similar to pirfenidone. The National Jewish Health statistician will hold the randomization schedule and the clinical research unit will keep the unidentified placebo or drug bottles for each patient prepared by Genentech. On the Day 1 visit, each subject will receive his or her first bottle of assigned unidentified drug.

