### **Biomarkers in blood**

The study will include a significant exploratory component focused on identification of biomarkers that may be prognostic for patients likely to have an accelerated rate of disease progression or diagnostic for identifying patients likely to benefit from treatment. Certain biomarkers may be differentially expressed in FHP and may change as a result of pirfenidone treatment. The blood samples that will be obtained for this study may help identify these biomarkers. Serum and plasma samples will be collected at baseline and at week 52 to assess the relationship between FHP related biomarkers (identified by RNA-seq and ChIP-seq), disease progression, clinical status, and treatment benefit. We hypothesize that distinct peripheral blood mononuclear cells gene expression profiles have the potential to be an adjunct to the traditional clinical-radiologic-pathologic assessment, in providing disease-specific prognostic information and help identify novel pathways for targeted therapy.

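### The plan names no arm-by-time contrast for gene-expression change, and the within-arm ANOVA it does state cannot show a drug effect in arms of unequal size

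*Combined protocol and SAP*

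**What the plan says.** The Biomarkers in blood section of the protocol has serum and plasma taken at baseline and Week 52. It says that certain biomarkers may be differentially expressed in FHP and "may change as a result of pirfenidone treatment", and it lists treatment benefit among the things to which biomarkers will be related.

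The analysis is in Statistical Methods, Exploratory Outcome Variables. RNA-seq and ChIP-seq results go through DESeq2, with Wald tests adjusted by Benjamini-Hochberg, and the significant genes are then assigned to pathways. No design formula, contrast or false discovery rate level is given. The closing sentence is the only one that names both expression time points. It says that the profiles "will be correlated within the two HP arms using an ANOVA analysis".

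In the same section, the questionnaires and the quantitative CT outcome each get a separate intercept per subject, a time-point effect and a time-point by treatment interaction.

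On numbers, Sample Size and Power Considerations states that "approximately 42 subjects will be enrolled and randomized in a 2:1 ratio to pirfenidone 2403 mg/d or placebo", and that "about 13 patients in the placebo and 25 (N=38) in the treatment group will provide at least 85% power".

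**The concern.** Whether a transcript changes because of pirfenidone is a question about the difference between arms in change from baseline. A test inside one arm also picks up natural progression, changes in background immunosuppression, regression to the mean and batch differences between the two sampling times. Only the comparison with placebo removes these.

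Allocation adds a second problem. Under 2:1 randomization the same true change is easier to detect in the pirfenidone arm. A gene that is significant on pirfenidone and not on placebo may then reflect a drug effect or only the larger sample, and within-arm analysis cannot tell the two apart. If per-arm results were read as drug effects, or passed on to pathway analysis in that sense, the conclusions would have no randomized support.

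**Working it through.** **1. Arm sizes.** Inputs from Sample Size and Power Considerations: 38 evaluable patients (25 and 13), 10% attrition, about 42 randomized 2:1.
- 38 / 0.9 = 42.2 and 38 × 1.1 = 41.8, so the plan's 42 is reproduced.
- 42 × 2/3 = 28 pirfenidone and 42 × 1/3 = 14 placebo. The documents do not print these two figures.
- Paired samples at both times would be nearer 25 v 13.

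**2. Power to detect the same change within each arm.** For a paired change of d standard deviations (SD of the within-patient change), the test is a one-sample t-test with n − 1 degrees of freedom and noncentrality d√n. For d = 0.5 the noncentrality is 0.5 × √28 = 2.65 v 0.5 × √14 = 1.87. The values of d are assumptions, because the documents give none.

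| Change in both arms | Two-sided level | 28 v 14 | 25 v 13 |
|---|---|---|---|
| 0 | 0.05 | 5% v 5% | 5% v 5% |
| 0.3 SD | 0.05 | 33% v 18% | 30% v 17% |
| 0.5 SD | 0.05 | 72% v 41% | 67% v 38% |
| 0.8 SD | 0.05 | 98% v 79% | 97% v 75% |
| 0.5 SD | 0.001 | 18% v 4% | 14% v 3% |
| 0.8 SD | 0.001 | 70% v 19% | 60% v 16% |

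The 0.001 rows stand in for a multiplicity-adjusted threshold.

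**3. Chance of significance in one arm only, when both arms change equally.** The arms are independent, so the probabilities multiply.
- 0.5 SD at 0.05, 28 v 14: pirfenidone only 0.723 × (1 − 0.410) = 43%; placebo only 0.410 × (1 − 0.723) = 11%.
- 0.5 SD at 0.05, 25 v 13: 0.670 × 0.618 = 41%; 0.382 × 0.330 = 13%.
- 0.8 SD at 0.001, 28 v 14: 0.698 × 0.812 = 57%; 0.188 × 0.302 = 6%.
- 0.8 SD at 0.001, 25 v 13: 0.603 × 0.845 = 51%; 0.155 × 0.397 = 6%.

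**4. With Benjamini-Hochberg.** This simulation used 15,000 independent genes, 1,500 of them changing equally in both arms, normal log-expression changes, a false discovery rate of 5% and 60 replicates per scenario. All of these settings are assumptions, and paired t-tests were used rather than DESeq2. The table gives the mean number of significant genes.

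| Change | Pirfenidone v placebo, 28 v 14 | Pirfenidone v placebo, 25 v 13 | Between-arm contrast of change |
|---|---|---|---|
| 0.3 SD | 1.4 v 0.1 | 0.9 v 0.1 | below 0.1 |
| 0.5 SD | 283 v 3 | 164 v 1 | below 0.1 |
| 0.8 SD | 1,346 v 290 | 1,223 v 176 | below 0.1 |
| 1.0 SD | 1,540 v 865 | 1,510 v 724 | 0.1 or fewer |

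No drug effect was simulated, so a contrast count near zero is the right answer. With 28 v 14, the larger arm had more significant genes in every replicate at 0.5 SD and above, but in only 53% of replicates at 0.3 SD. When no gene changes, both arms average about 0.1 genes or fewer.

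**The case against.** The strongest reply is that the text is ambiguous, not shown to be wrong. Correlating profiles within arms by ANOVA is not a defined per-gene test, and an ANOVA could carry arm and time terms. The gene lists and the pathway step follow from the DESeq2 tests, and the ANOVA sentence is separate. Since the DESeq2 design is not given, it might already contain patient, time and an arm-by-time term. The biomarker section also has prognostic aims that need no treatment contrast.

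Much of this stands, and it rules out several stronger readings that a reader might infer:
- That DESeq2 will use the wrong contrast or ignore the pairing. The plan is silent on both.
- That the pathway analysis will be built on within-arm lists. The text does not link the two.
- That gene counts will be compared between arms. No such comparison is planned.
- That the pirfenidone arm is bound to show more genes. This fails when nothing changes and is weak at 0.3 SD.
- That a gene significant only on pirfenidone is an artefact of arm size. It could be a real effect; the within-arm analysis cannot say which.

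The magnitude is also open to challenge. The 72% v 41% uses an unadjusted level and an assumed effect; at 0.001 the same 0.5 SD change gives 18% v 4%.

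The reply does not remove the point. The only analysis stated for the two time points is within arms, no between-arm contrast of expression change appears anywhere, and the neighbouring outcomes in the same section do have one. A plan that fits both a valid and an invalid analysis should name its model before unblinding.

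**Conclusion.** The concern holds in limited form. For expression change, the plan states a within-arm ANOVA and leaves the DESeq2 design and contrast open, while part of the biomarker aim concerns the effect of pirfenidone. Within-arm results from arms of about 28 v 14, or 25 v 13 evaluable, cannot answer that part. If genes truly change by the same moderate amount in both arms, the larger arm would tend to yield more significant genes.

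The size of this tendency depends on how many genes change and by how much. The documents give neither, so the figures above are illustrations over a range. What needs no assumption is that a within-arm test makes no use of the randomized comparison. No efficacy or safety conclusion depends on this analysis, so the priority is low.

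**What to change.** Replace the within-arm ANOVA sentence with one paired DESeq2 model per gene, with terms for patient nested in arm, time (baseline or Week 52) and arm-by-time. Then:
- test the arm-by-time term with the Benjamini-Hochberg adjustment already planned, and state the false discovery rate level;
- base any statement or pathway analysis about drug effect on that term alone;
- keep within-arm changes descriptive, with estimates and intervals.

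This is a change of wording before unblinding, with the same samples and software. It brings expression into line with the interaction already specified for the questionnaires and quantitative CT.

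The cost is fewer declared genes, because interaction power is low at this size. As an approximation, take a two-sample t-test on the change with noncentrality δ / √(1/28 + 1/14), where δ is the between-arm difference in SDs of change. For δ = 0.5 the noncentrality is 1.53, which gives 32% power at 0.05 and 3% at 0.001. For δ = 1.0 the figures are 85% and 33%. The report should therefore say that a short or empty gene list is not evidence that the drug has no effect on expression.
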